#### 1.3 SAMPLE SIZE, TIMELINE, AND ENDPOINTS

#### SAMPLE SIZE

We anticipate that approximately 200 patients will participate in this study. Randomized clinical trial of CPAP (n=100) vs. control (n=100) in COVID-19 suspected or confirmed patients with abnormal chest x-ray or respiratory symptoms.

#### **TIMELINE**

We anticipate that accrual will occur over a 1-3 month period, beginning as soon as IRB approval is obtained. The study will last until we have 100 participants in each group, and each group completes all phases of the trial.

#### **ENDPOINTS**

#### **Primary endpoint:**

The primary efficacy endpoint is a non-weighted composite endpoint comprised of the following components;

- All-cause mortality within 14 days of randomization
- Hospital Admission (including ED visit) within 14 days of randomization
- Oxygen saturation less than 90 during the 72-hour observation period from randomization
- Absolute reduction in oxygen saturation of more than 4% during the 72-hour observation period from randomization

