saturation and a disposable home sleep apnea monitor (WatchPAT) to track blood oxygen level continuously for 12 hours with data feed into a cloud based platform. Additionally, 100 patients will be randomized to receive CPAP at fixed pressure of 8 cm in women and 10cm in men and obese men and women will start be set at 10cm. of water pressure for 72 hours continuously (except for daily activities such as eating, grooming etc). We will adjust pressures in the range of 8-10cm depending on patient's comfort and related assessments in follow up period. However, the range of the pressure will remain constant throughout the study. While the study protocol will end at 72 hours, patients who wish to continue CPAP will be allowed to do so for symptomatic benefit up to 7 days from randomization. All CPAP recipients will be given a full-face mask and will be asked to stay in quarantine for the duration of the protocol to avoid risk of infecting family members with aerosol (information on this presented below). We hypothesize that early CPAP in COVID infected patients who have respiratory abnormalities will decrease the risk of subsequent hospitalization or death in 14 days from randomization.

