#### **OBJECTIVES**

Aim 1: Given the expected shortage of ventilators to treat COVID-19 suspected or confirmed individuals with severe acute respiratory distress syndrome (SARS)/ARDS, we propose a prospective, single-center, parallel group, open label, randomized clinical trial of CPAP (n=100) vs. control (n=100) in COVID-19 suspected or confirmed patients with abnormal chest x-ray or respiratory symptoms. The overarching aim of this proposal is to determine if early use of CPAP at home reduces the need for hospitalization admission or death in COVID-19 suspected or confirmed patients. We will include adult patients (age>18), oversampling when possible for obese patients who live alone or have more than one bedroom at home, with serologically confirmed or under investigation for acute COVID-19 infection, who have one or more of the following: fever (>38°C), sore throat, myalgia or flu-like illness AND have one or more of the following additional symptom or diagnostic criteria: abnormal chest x-ray, new onset cough, mild hypoxemia at rest (saturation less than 96%), abnormal lung exam, chest tightness or shortness of breath AND who are without need for hospital admission, i.e. being sent home. Patients with preexisting pulmonary diseases such as advanced COPD, advanced parenchymal lung disease, history of pneumothorax etc. will be excluded (see inclusion and exclusion criteria for more information). Participants in both arms will be shipped a pulse oximeter to monitor oxygen saturation and a disposable home sleep apnea monitor (WatchPAT) to track blood oxygen level continuously for 12 hours with data feed into a cloud based platform. Additionally, patients in the treatment arm (n=100) will be randomized to receive CPAP at fixed pressure: 8 cm water pressure in women and 10cm water pressure in men. All obese patients (BMI>=30) will be treated with a fixed pressure of 10cm of water pressure (both men and women). The CPAP pressure will be adjusted based on patient's comfort but will not deviate from the range of 8-10cm noted above. The treatment will be prescribed for 72 hours continuously (except for daily activities such as eating, grooming etc). While the study protocol will end at 72 hours, patients who wish to continue CPAP will be allowed to do so for symptomatic benefit up to 7 days. All CPAP recipients will be given a full-face mask and will be asked to stay in quarantine for the duration of the protocol to avoid risk of infecting family members with aerosol. We hypothesize that initiation of early CPAP in COVID infected patients with respiratory abnormalities will decrease the risk of subsequent hospitalization or death in 14 days from randomization. Patients will be followed for 28 days and as a secondary endpoint we will assess 28 day mortality as well as to assess for late impact of CPAP.

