
Aim 2: Younger Americans with COVID-19 infection have a higher rate of hospitalization and need for mechanical ventilation compared to younger citizens of other countries. One potential explanation is high obesity prevalence. Obstructive sleep apnea is present in over 50% of obese individuals and obesity further compromises lung compliance and ability to handle increased ventilatory demand seen in COVID-19 patients with related lung injury. Further, COVID infected individuals with OSA may be at higher risk for progression from mild pneumonia to ARDS however this remains to be determined. Therefore in Aim 2, we will determine if obstructive sleep apnea (OSA) is associated with increased hospitalizations and mechanical ventilation in COVID-19 suspected or confirmed patients. This will be achieved primarily through our control group (not receiving PAP therapy but will receive home sleep apnea testing). This is of vital importance as the primary treatment of OSA is CPAP and there are more than 8 million CPAP users in the United States. This treatment can therefore be leveraged to treat mild respiratory distress in COVID infected OSA patients in the face of a crisis with hospital and ventilator shortage. We hypothesize that obese patients with COVID-19 infection are more likely to be hospitalized or receive mechanical ventilation compared to non-obese individuals with COVID-19 infection. In exploratory analysis, we will also assess if OSA is an independent risk factor for hospital admission or death in our control group. We expect obesity and OSA to be correlated and will determine the independent impact of each of these on our primary endpoint.

**Aim 3:** To leverage EHR to determine a risk score to predict readmission to the Emergency room in COVID-infected or suspected patients. This aim will be done simultaneously while Aims 1 and 2 are ongoing and will be implemented in real-time to identify high-risk patients.

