#### **Secondary endpoints:**

• Time to ICU admission within 14 days of randomization

- Time to intubation and mechanical ventilation within 14 days of randomization
- Time to death within 14 and 28 days of randomization
  - Degree of improvement in oxygen saturation within 14 days of randomization
  - Improvement in respiratory symptoms of cough, shortness of breath, etc via respiratory symptom questionnaire within 14 days of randomization
  - Adverse events and conversion rates of COVID family members in CPAP vs control within 14 days of randomization
  - Percent of patients electing to continue CPAP for greater than 72 hours
  - Time to hospital admission or ED visit within 14 days of randomization

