#### 7.1 VISIT SCHEDULE

#### Study Procedures:

- 1) Patients will be screened as described earlier
- 2) Eligible patients will be provided a flyer by ED provider when possible but may also be contacted by telephone once they have been discharged. (Of note: we are being approached by patients who are discharged from the hospital with COVID pneumonia who continue to experience shortness of breath and are requesting a CPAP without having prior knowledge of this study).
- 3) Research will be introduced to the patient, and if they agree to participate, a telephone consent will be conducted (according to IRB requirements including witness). Once patients have enrolled in the study, their PMD will also be notified of their participation. The patient will also be added to the study on EPIC, so that all treating physicians are aware of the patient's participation in our study.
- 4) Once patients have enrolled in the study, a pulse oximeter and a disposable WatchPAT One device will be mailed to the patients (within 24-48 hours of discharge). Orders placed before noon will be delivered the same day by a local durable medical equipment company we are working with. Orders placed past noon, CPAP delivery will be done the subsequent day or upto 48 hours if outside the New York area. Patients who are randomized to the treatment arm will receive a CPAP machine and three full-face masks in addition to the above noted equipment.
- 5) Patient will then be instructed via facetime or other video platform on CPAP setup and use, face mask fitting (those randomized to CPAP), and use of the WatchPAT One and pulse oximeter (for both CPAP and control arm). All participants will wear the WatchPAT one for one night whereas the oximeter will stay on continuously and the patient will report the saturation to us via follow up survey.
- 6) Patients randomized to receive CPAP will be asked to stay in isolation throughout the duration of the study i.e. 72 hours. They will be required to stay in a different room with the door shut and windows open (weather permitting). We will also ask the patient to stop using CPAP during meals or other daily activities. Subjects not on CPAP machine will also be instructed to sleep in a room with windows open (weather permitting).
- 7) Patients will use the CPAP machine as instructed for 72 hours.

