- 8) All patients will be contacted every 6-12 hours to complete follow up assessments. These follow ups will be done via a phone call. If the timing of these follow ups fall between 10pm-6am, the follow up will be deferred until after 6am. After 72 hours, all patients will then be contacted daily until day 14 from randomization. After day 14, research staff will continue to monitor the medical charts for any visits to the hospital. One last contact will be made on day 28.
- 9) After 72 hours, patients will be asked to discontinue using the CPAP and pulse oximeter. If patients wish to continue to use the CPAP, they may do so for up to 7 days from time of randomization.
- 10) The research staff will continue to call all patients daily (after the 72 hour mark) to assess symptoms.
- 11) The patients can also choose to monitor their oxygen saturation beyond the 72 hours of treatment.
- 12) CPAP download is available continuously however we will download data on usage, pressure, leak daily and make adjustments to the mask or CPAP pressure as needed for patient comfort. For patients experiencing significant trouble tolerating high pressure, we will decrease CPAP from 8-10 cm to a fixed CPAP of 5 cm for 2-4 hours after which we will raise it back to 8-10cm for the

- duration of the study. If the patient is not able to tolerate the pressure again, we will reduce it back to 5cm of water pressure for several hours before increasing the pressure. This will be continued until the patient withdraws or 72 hours are completed, whichever occurs first.
- 13) Patients will be asked to track their own oxygen saturation using the provided pulse oximeter and report it when we contact them for the 6-12 hour follow up calls/surveys.
- 14) The sleep apnea test will provide continuous oxygen and breathing data for a period of 12 hours during the 72 hours and will also provide information on oxygen saturation while the patient is asleep.

The outline of the forms that correspond to the study visits can be found in the Appendix, Figure 1. All of these forms are subsequently included in the following appendicies.

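### Aim 2's unadjusted control-arm tests cannot give the promised independent impact of OSA and obesity, and no between-arm analysis tests the stated day-14 hypothesis of hospitalization or death

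*Protocol*

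**What the plan says.** **Aim 2.** Protocol 1.2, Objectives, states that "Obstructive sleep apnea is present in over 50% of obese individuals" and then: "We expect obesity and OSA to be correlated and will determine the independent impact of each of these on our primary endpoint". The hypothesis it states formally is about obese versus non-obese patients. The question of OSA as an independent risk factor for admission or death in controls is labelled exploratory. The SAP, under Exploratory Analyses, applies the primary method to controls only, once for OSA and once for obesity. The primary method is an unadjusted two-sided Fisher's exact test. No regression or stratified analysis is named.

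**The trial hypothesis.** Protocol 1.2 hypothesises that early CPAP "will decrease the risk of subsequent hospitalization or death in 14 days from randomization". The primary composite (protocol 1.3; SAP, General Design Issues) has four components: death by day 14, admission or ED visit by day 14, saturation below 90 in the 72 hours from randomization, and "Absolute reduction in oxygen saturation of more than 4% during the 72-hour observation period from randomization". Secondary endpoints include "Time to hospital admission or ED visit within 14 days of randomization", and time to death. The SAP analyses admission/ED by a log-rank test, or Gray's test with death as a competing risk, and survival by a separate log-rank test.

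**Saturation.** For the CPAP arm, "The treatment will be prescribed for 72 hours continuously (except for daily activities such as eating, grooming etc"). Protocol 7.1 says that "the oximeter will stay on continuously and the patient will report the saturation to us via follow up survey". It also describes a 12-hour WatchPAT recording within the same 72 hours. In the Clinical Endpoints table of section 10 the fall of more than 4% is tied to breathing symptoms; in protocol 1.3 and the SAP it is not.

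**The concern.** Two stated questions do not match their planned analyses.

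For Aim 2, when two risk factors are correlated, an unadjusted comparison on one carries part of the effect of the other. If obesity raises risk and OSA does not, OSA patients will still show more events because more of them are obese. The reverse holds for obesity. Two separate Fisher tests can both be correct as descriptions of crude association and still say nothing about independent impact.

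For the trial hypothesis, a positive composite could be driven by any of its four components. The reader will want to know whether hospitalization or death moved, and no planned between-arm analysis reports that outcome. This matters more because the saturation components are observed while only one arm is prescribed pressure. Part of a difference in the composite may therefore reflect readings taken on CPAP.

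**Working it through.** **1. The plan's own figures.** Exact power of the two-sided Fisher test at 0.05, 100 per arm, by full enumeration of two binomials:

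| Control / CPAP | 25/9 | 30/12 | 35/16 | 40/20 | 45/25 | 50/29 |
|---|---|---|---|---|---|---|
| Power (%) | 83.0 | 85.4 | 84.3 | 84.5 | 80.9 | 83.3 |

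All exceed 80%. The SAP's power table is right and is not in question.

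**2. Aim 2: how far the crude OSA test moves with no OSA effect.** From the documents: 100 controls, two-sided Fisher at 0.05, a 25% event rate (lower end of the SAP's control range), and OSA in over 50% of obese patients, taken here as 50%. Assumptions: half of controls are obese; OSA is present in a share q (0 to 20%) of the non-obese; event risk depends on obesity only, at 35% vs 15% or 30% vs 20%.

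There are 25 obese OSA patients and 50q non-obese OSA patients. With obese and non-obese risks p1 and p0:

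- risk in OSA = (25·p1 + 50q·p0) / (25 + 50q)
- risk in non-OSA = (25·p1 + (50 − 50q)·p0) / (75 − 50q)

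Example, 35% vs 15% with q = 0: OSA 35%; non-OSA (8.75 + 7.5)/75 = 21.7%.

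| q | OSA vs non-OSA patients | Rejects, 35/15 | Rejects, 30/20 |
|---|---|---|---|
| 0 | 25 vs 75 | 22.7% | 8.5% |
| 10% | 30 vs 70 | 15.1% | 6.7% |
| 20% | 35 vs 65 | 9.3% | 5.2% |

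A logistic model with both factors, tested by likelihood ratio for OSA (20,000 simulations per cell), rejects in 5.2% to 5.6% throughout.

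**3. What the joint model can deliver.** With q = 0 only obese patients inform the OSA effect, so SE of the log odds ratio = √(2 / (25·p1·(1 − p1))). At p1 = 0.35 this is √(2/5.69) = 0.593, and exp(1.96 × 0.593) = 3.2. Across all six cells at 25 events the SE is 0.506 to 0.617, a factor of 2.7 to 3.35 each way. At 50 events (the SAP's upper control rate, with an assumed 60% vs 40% by obesity) and q = 0, SE = √(2/(25 × 0.24)) = 0.577, a factor of 3.1. More events alone do not make the interval narrow.

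**4. Which planned between-arm analysis covers death or admission?**

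| Planned analysis | Death | Admission/ED | Anything else |
|---|---|---|---|
| Primary composite | yes | yes | two saturation components |
| Time to admission/ED | competing risk only | yes | no |
| Survival, days 14 and 28 | yes | no | no |
| Time to ICU, intubation | competing risk only | no | ICU, ventilation |

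None covers death and admission together and nothing else.

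**5. Precision of the missing analysis.** Take 25% in controls, the SAP's preliminary hospitalization figure, as an assumption for death or admission. Exact Fisher power is 0.83 for 25% vs 9% and 0.44 for 25% vs 14%. At 25% in both arms the 95% half-width of the risk difference is 1.96·√(2 × 0.25 × 0.75/100) = 0.12.

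**6. Would that test show where a composite difference came from?** Assume saturation-only events among patients without death or admission, and simulate both tests in the same trials. The last column is the share of composite rejections in which the death-or-admission test does not reject.

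| Death/admission, control vs CPAP | Saturation-only in the rest | Composite, control vs CPAP | Composite rejects | Share |
|---|---|---|---|---|
| 25 vs 25 | 10% vs 7.5% | 32.5 vs 30.6 | 4.2% | 60% |
| 25 vs 25 | 20% vs 10% | 40 vs 32.5 | 15.6% | 90% |
| 25 vs 25 | 10% vs 10% (no on-mask effect) | 32.5 vs 32.5 | 3.4% | 55% |
| 25 vs 25 | 20% vs 20% (no on-mask effect) | 40 vs 40 | 3.6% | 70% |
| 25 vs 14 | 20% vs 11% (benefit on all) | 40 vs 23.5 | 66% | 40% |

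Discordance is common with no on-mask effect and with a real benefit on everything, so it does not identify the source.

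**7. Baseline for the fall in saturation.** The study oximeter is ordered after randomization (protocol 7.3). The only earlier saturation on the forms shown is the ED chart value, recorded with or without supplemental oxygen. Delivery may take up to 48 hours (protocol 7.1), which could leave about 72 − 48 = 24 hours of the window. No baseline is named, and no rule says whether WatchPAT values count.

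**The case against.** **On-treatment saturation may be genuine benefit.** This stands. Scoring saturation during therapy is a design choice. A reader might infer that the primary test is biased or that its null hypothesis would be falsely rejected. The documents do not support that: the null concerns the composite as defined, and they give no size for any on-mask effect. A reader might also infer that mask status goes unrecorded. That is not established either: "CPAP download is available continuously however we will download data on usage, pressure, leak daily", a CPAP Use Form is completed at the check-ins, and the contents of the form are not in the published text.

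**The reporting route is stated.** Also true. Oximeter values are reported at the scheduled calls. What is missing is the link from those values to the endpoint, the baseline, and the place of WatchPAT.

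**Death or admission will nearly equal admission/ED.** Largely true. The SAP expects mortality below 2.99%, so few deaths without admission will separate the two. The added analysis matters because it is the stated hypothesis, not because it will look very different.

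**Aim 2 is low-stakes and the joint model is imprecise.** The independent OSA question is partly labelled exploratory, the crude comparison does answer the stated obesity hypothesis, and the inflation is negligible at the mild end (5.2%). But the protocol promises independent impact on the primary endpoint without that qualification, and an imprecise estimate of the right quantity is better than a test of a different one.

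**The >4% wording sits in an adverse-event table.** Yes, but under a heading on clinical endpoints. This is minor.

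**Conclusion.** Two mismatches hold on the documents.

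1. The Aim 2 analysis cannot separate OSA from obesity. Under the prevalences and risks assumed above, the crude OSA test rejects in about 5% to 23% of trials with no OSA effect. The upper figure needs no OSA at all among the non-obese and a 20-point obesity effect. These are rejections of a true crude difference; the error would be to read them as independent impact.
2. No between-arm analysis tests hospitalization or death by day 14 as one outcome, although that is the trial's hypothesis. The components are analysed, but not jointly.

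The saturation point is lesser: the fall of more than 4% has no named baseline, and two of the four components are scored while only the CPAP arm is prescribed pressure. It is tempting to go further and say that adding a death-or-admission test would reveal whether a positive composite came from on-mask readings. It would not: at power 0.44 for 25% vs 14%, a non-significant result is compatible with a real benefit.

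**What to change.** **(a) SAP, Exploratory Analyses.** Add one logistic model in controls containing both OSA and obesity. Report odds ratios with 95% intervals on the primary composite and on hospital admission or death, the two outcomes Aim 2 names for this question. Keep the unadjusted obese versus non-obese comparison for the stated obesity hypothesis. Cost: one paragraph. With about 25 to 50 control events the intervals are wide, so present estimates and not a decisive test.

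**(b) SAP, secondary analyses, and protocol 1.3.** Add death or hospital admission (including ED visit) by day 14 as a key secondary analysis, compared by arm with the same Fisher test and reported with the risk difference and 95% interval. Tabulate each composite component by arm. Cost: one paragraph and no new data. State in advance that a non-significant result does not locate the source of a composite difference.

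**(c) Protocol 1.3 and SAP endpoint definition.** Name one baseline source for the fall in saturation, the same in both arms, and say how events are scored before equipment arrives. Each option has a drawback: the ED value may be on supplemental oxygen, and a value taken at equipment set-up is post-randomization and absent for patients with earlier events. State whether WatchPAT values count. Reconcile the >4% wording in protocol 1.3, the Clinical Endpoints table and the SAP, or say that the table governs adverse-event reporting only.

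These changes concern scoring and analysis only. They need no extra patients or visits.

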#### **Secondary endpoints:**

• Time to ICU admission within 14 days of randomization

- Time to intubation and mechanical ventilation within 14 days of randomization
- Time to death within 14 and 28 days of randomization
  - Degree of improvement in oxygen saturation within 14 days of randomization
  - Improvement in respiratory symptoms of cough, shortness of breath, etc via respiratory symptom questionnaire within 14 days of randomization
  - Adverse events and conversion rates of COVID family members in CPAP vs control within 14 days of randomization
  - Percent of patients electing to continue CPAP for greater than 72 hours
  - Time to hospital admission or ED visit within 14 days of randomization

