- Improvement in oxygen saturation will be compared between randomization groups using linear mixed-effect models with patient as a random effect.
- Improvement in respiratory symptoms, as measured by the Clinical COPD Questionnaire, will be compared between randomization groups using linear mixed-effect models with patient as a random effect.

Conversion rate of family members

The conversion rates (yes/no) of family members in the two randomization groups will be compared using a Fisher's exact test. If there is sufficient variability, a zero-inflated count model may be considered as well.

Continuation of CPAP for greater than 72 hours

The proportion of patients in the CPAP group who elected to continue CPAP use after 72 hours will be estimated along with 95% Coppler-Pearson confidence intervals.

Exploratory Analyses

Exploratory analyses will be conducted similarly as the primary analysis except that it will be only in the control arm comparing OSA versus non-OSA patents and obese vs non-obese patients.

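### The oxygen-saturation secondary endpoint runs to day 14, but no saturation reading is required after 72 hours

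*Protocol*

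**What the plan says.** Protocol section 1.3 (Secondary endpoints) lists "Degree of improvement in oxygen saturation within 14 days of randomization".

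Protocol section 7.1 sets out how saturation is measured:

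- Item 5, for both arms: "the oximeter will stay on continuously and the patient will report the saturation to us via follow up survey".
- Item 13: patients track their saturation and "report it when we contact them for the 6-12 hour follow up calls/surveys". Under item 8 those calls give way to daily calls after 72 hours.
- Item 9: "After 72 hours, patients will be asked to discontinue using the CPAP and pulse oximeter".
- Item 10: "The research staff will continue to call all patients daily (after the 72 hour mark) to assess symptoms". Saturation is not mentioned.
- Item 11: "The patients can also choose to monitor their oxygen saturation beyond the 72 hours of treatment".
- Item 14: the WatchPAT gives 12 hours of oxygen data, inside the 72 hours.

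Section 7.6 keeps the Follow-up Questionnaire on days 4-7, both for patients on CPAP and for those not on it. Section 7.7 does not list it for days 8-14. The forms named there are the Respiratory Questionnaire, the Interval Assessment and, on day 28, the Investigator Statement.

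SAP, Respiratory Function: "Improvement in oxygen saturation will be compared between randomization groups using linear mixed-effect models with patient as a random effect". No window, time points or handling of optional readings is given. The SAP's rule for missing data covers the primary outcome only.

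**The concern.** The endpoint covers two weeks, but the plan secures measurement for three days at most. Whatever saturation data exist after that come from patients who decided to go on measuring after being asked to stop.

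That decision need not be neutral between arms. Patients know their allocation, and only those on CPAP may extend treatment to day 7, which may give them a reason to keep the oximeter in use. If the decision also depends on how the patient is doing later, the comparison partly reflects who kept measuring.

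There is a second cost even if no such bias exists. With no window in the SAP, the analyst must decide after the data are in whether the model stops at 72 hours or runs to day 14, and which voluntary readings count.

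**Working it through.** **The plan's own figures.** The documents give no power or precision for this endpoint. The SAP's only power figures belong to the primary endpoint. Recomputed with the exact two-sided Fisher test at 100 per arm, the six scenarios give 83.0, 85.4, 84.3, 84.5, 80.9 and 83.3%, all above 80% as stated. Nothing below changes them.

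**Step 1: coverage.** Endpoint window: 14 × 24 = 336 hours (section 1.3). Required oximetry: 72 hours (section 7.1, item 9).

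- Covered: 72/336 = 21%.
- Not covered: 336 − 72 = 264 hours; 264/336 = 11/14 = 79%.

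Three days is a ceiling. Equipment is ordered after randomization (section 7.3) and can take up to 48 hours to arrive (section 7.1, item 4), so if the 72 hours run from randomization, coverage is shorter.

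**Step 2: what each period offers.**

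| Days | Saturation reading | Listed route for reporting it |
|---|---|---|
| 1-3 | Required, both arms; WatchPAT for 12 hours | 6-12 hour calls, Follow-up Questionnaire |
| 4-7 | Optional | Follow-up Questionnaire, both arms |
| 8-14 | Optional | Follow-up Questionnaire not listed; contents of the listed forms not shown |

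**Step 3: how far optional readings can drift (assumed inputs).** Suppose a share p of an arm keeps measuring, and the tendency to do so has correlation r with worse saturation. Under a normal threshold model the mean of those who continue is lower by r × φ(z_p)/p standard deviations.

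- p = 0.8, r = 0.2: 0.2 × 0.280/0.8 = 0.07 SD.
- p = 0.2, r = 0.5: 0.5 × 0.280/0.2 = 0.70 SD.

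The bias between arms is the difference between the two arms' shifts. It is zero if selection is the same in both.

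**Step 4: what the mixed model would do (assumed inputs).** Take a deliberately extreme case with no treatment effect. The true late mean is 95% in both arms; everyone continues in one arm, and only the sicker half (mean 93.5%) in the other. The raw late difference is 95.0 − 93.5 = 1.5 points. For a normal distribution cut at its mean, this implies a between-patient SD of 1.5/0.798 = 1.88.

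A model with a patient effect also uses each patient's early readings. The late-period bias that remains is roughly 1.5 × (1 − R²), where R² is the share of late severity that the early readings predict. If severity is stable, with six early readings (the six windows in the Visits Figure) and within-patient SD s, then R² = 1.88²/(1.88² + s²/6).

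- s = 1: R² = 3.53/(3.53 + 0.167) = 0.955; remaining bias 1.5 × 0.045 = 0.07 points.
- s = 2: R² = 3.53/(3.53 + 0.667) = 0.841; remaining bias 1.5 × 0.159 = 0.24 points.
- If late severity is unrelated to the early readings, R² = 0 and the full 1.5 points remain.

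The result therefore turns on two things the documents do not give: whether continuation differs by arm, and how much of the change after 72 hours the early readings fail to predict.

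**The case against.** Several points on the other side are sound.

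- **Collection does not simply stop at 72 hours.** A reader might infer that no saturation data can reach the study after that, or that the later forms lack a field for it. The documents do not support this. The Follow-up Questionnaire runs to day 7 in both arms, and the contents of the Interval Assessment and the questionnaires are not shown. What the text supports is that later readings are not required.
- **The raw 1.5-point difference is not a forecast.** It comes from extreme assumed selection, and the planned analysis would not compare raw late means. With stable severity the model removes most of it (Step 4). No passage shows that continuation will differ by arm.
- **Late deterioration is not lost to the trial.** A reader might link the 72-hour limit to the Introduction's remark that decompensation comes 7-10 days after symptoms begin. Death and hospital or ED attendance are in the primary endpoint to day 14, and ICU admission and intubation are secondary endpoints over the same period.
- **The endpoint wording might be satisfied by early data.** It could mean any improvement seen up to day 14, which 72-hour readings would partly serve. Neither document says so.

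What survives is the mismatch itself. A questionnaire that can carry an optional reading does not make it a required one, and item 9 has already asked patients to stop.

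**Conclusion.** The endpoint window and the measurement schedule disagree, and the SAP does not settle which governs. About 11 of the 14 days (79%) have no required saturation reading. This follows directly from sections 1.3 and 7.1 and needs no assumption about patient behaviour.

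Bias in the mixed-model comparison is possible but conditional. It needs continued measurement to differ by arm and to depend on later changes that early readings do not predict. Its size cannot be determined from the documents; the figures in Steps 3 and 4 show the mechanism under assumed inputs only.

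This is one secondary endpoint. The saturation components of the primary endpoint are already limited to the 72-hour period, so the primary analysis and the power table stand. The point should be corrected, but it does not threaten the trial's main conclusion.

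**What to change.** Reconcile Protocol section 1.3, section 7.1 (items 9, 11 and 13) and the SAP's Respiratory Function paragraph in one of two ways.

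**(a) Shorten the endpoint.** State the endpoint and the SAP model as covering 72 hours from randomization, and exclude voluntary later readings from the arm comparison. This is a wording change only. The cost is a shorter endpoint.

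**(b) Extend the measurement.** Ask both arms to keep the oximeter they already have and to report one reading at each daily call already scheduled to day 14. Record whether it was taken on or off CPAP, without asking patients to change their CPAP use for the reading. Make sure the forms for days 4-14 capture it. No new device or call is needed. The cost is slightly more burden on patients and an edit to the forms if the field is not already there.

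Under either option the SAP should name the time points in the model; under (b) it should also say how missed readings are handled. The choice should be made before any comparison by arm.
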